5.4 Safety Outcomes

Safety outcome variables will consist of rate of adverse events in general.

6. STUDY DESIGN

6.1 General study design and justification of design

This is a single center clinical study comparing effects of CBD e-liquid versus a perfumed e-liquid on physiological processes (episodic memory) in healthy subjects using the following design

- Randomized
- Double-blind
- Placebo-controlled
- Cross-over design
- Approx. equal number of male and female subjects in each group

The duration of the study - from first participant in to last participant out - lasts approximately 6 months. The duration for a participant will be approximately 80 minutes for visit 1, and 45 min for visit 2. Dropouts will be replacement until data of total needed sample size is completed.

The wash-out period between the two testing days lasts 14 days (approximately 10 half-lives of CBD (Ujvary & Hanus, 2016)) to 56 days (due to flexible recruiting).

6.2 Methods of minimising bias

6.2.1 Randomisation

By time of visit 1 eligible participants will be randomly allocated to receive either CBD or placebo (perfumed e-liquid) first. To minimise allocation bias, a randomization list will be prepared by a team member of the division of cognitive neuroscience. Block randomization will be used to achieve balance between number of participants starting with CBD and number of participants starting with placebo. A separate list will be used for males and females. The randomization number will be listed in the SD and in the eCRF.

6.2.2 Blinding procedures

CBD e-liquid and perfumed e-liquid will be filled in identically looking vaporization tanks and labelled with a randomization number. Furthermore, tanks are wrapped with transparent colorized tape to cover e-liquid colour. Both vapes taste like citrus fruits. Participants will vape under supervision of a study member on a quiet balcony to avoid contaminating the air in the examination room with CBD vapours.

6.2.3 Other methods of minimising bias

The investigators of the test days will be trained personal and will follow detailed instructions to ensure that each test day will be conducted in a highly standardized way.

All study team members will be blinded to ensure that task evaluation by raters will be unbiased.

In order to minimise time of days effect, the time of day of all main visits will be keep constant (e.g. morning or afternoon) for each participant.

6.3 Unblinding Procedures (Code break)

Unblinding will be permitted under these circumstances

- SAE
- AE if knowledge is crucial for further medical approach

Unblinding procedures:

Randomization list containing unblinding information of each participant will be kept under the responsibility of the Sponsor-Investigator and unblinding of the participant can be performed by the Sponsor-Investigator at any time. The Sponsor-Investigator documents the unblinding. The

subinvestigator and other members of the team will not be informed about the result.

7. STUDY POPULATION

7.1 Eligibility criteria

Participants fulfilling all of the following inclusion criteria are eligible for the study:

- Healthy
- Normotensive (BP between 90/60mmHg and 140/90mmHg)
- BMI between 18 and 30 kg/m²
- Male or female
- Aged between 18 and 30 years
- Native or fluent German-speaking
- Able and willing to give written informed consent as documented by signature and comply with the requirements of the study protocol
- Willing to donate urine sample to control for pre-Visit CBD/THC consume

The presence of any one of the following exclusion criteria will lead to exclusion of the participant, for example:

- Acute or chronic psychiatric disorder including drug or alcohol abuse
- Women who are pregnant or breast feeding
- Intention to become pregnant during the course of the study
- Smoking (> 5 cigarettes per day)
- Participation in one of our previous studies using the same verbal test in the past 2 years
- Participation in a study with CBD / THC within the 30 days preceding and during the present study
- Known hypersensitivity or allergy to propylene glycol
- Intake of CBD / THC within the 7 days preceding and during the present study in any application form
- Long-term systemic medication or topical steroids to treat an underlying disease within last 3 months
- Inability to follow the procedures of the study, e.g. due to language problems, psychological disorders, dementia, etc. of the participant
- Enrolment of the investigator, his/her family members, employees and other dependent persons

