7.4 Criteria for withdrawal / discontinuation of participants

Participants have the right to withdraw from the study at any time for any reason without being obliged to give reason. There will be a final interview regarding their actual wellbeing after withdrawal for whatever reason. The subinvestigator also has the right to withdraw participants from the study if it is in the best interest of the participant.

The following reasons result in withdrawal:

- Adverse events prohibiting cognitive testing (e.g. nausea, headache)
- Single administration of psychoactive drug within 5 days before visit 2
- Non-Compliance
- Severe protocol violations
- Administrative problems
- Impossibility to vape 0.25mL e-Liquid
- Alcohol intake within 12 hours before visit 2

Withdrawal date and reason (if known) will be listed in the participant enrolment log. Safety data will be analysed for all participants, who received study medication.

A team member, who is not involved in the data sampling procedure, will provide the study leader with replacement e-liquid tanks, in case drop-outs have to be replaced. This way, the randomization order of the randomization list can be maintained. Drop-outs will be replaced until data of 34 participants are completed.

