8. STUDY INTERVENTION

8.1 Identity of Investigational Products (treatment / medical device)

8.1.1 Experimental Intervention (treatment / medical device)

Single vape of 0.25mL of CBD e-Liquid containing: 5% CBD (low-temperature extracted Cannabidiol from Cannabis sativa L., purity 99%), Glycerine (vegetable), Propylene glycol, water

Brant: Pharma Hemp, Slovenia, <https://pharmahemp.store/shop/e-liquids/cbd-e-liquid-5-10ml/>

Label: CBD E LIQUID 5% Citrus Fruits

Color: Light orange

Taste: Citrus Fruits

Vaporizer: Canna Vape Kit

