8.1.2 Control Intervention (standard/routine/comparator treatment / medical device)

Single vape of 0.25mL of La Baronne Jaune e-Liquid containing: Foodstuff fragrance additives, 80% Glycerine (vegetable), 20%Propylene glycol

Brant: BORDO2, France, <https://www.bordo2.com/oh-my-god/la-baronne-jaune-oh-my-god>

Label: LA BARONNE JAUNE

Color: Colorless

Taste: Lemon and madeleines

Vaporizer: Canna Vape Kit

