9.3 Procedures at each visit

9.3.1 Screening visit

During the screening – that is the first part of the first visit- the subinvestigator will again explain the nature of the study, its purpose, the procedures involved, the expected duration, the potential risks and benefits, and any discomfort it may entail. Furthermore, each subject will be informed that participation in the study is completely voluntary and that they can withdraw from the study at any time. Subjects will be informed that authorized individuals, other than the investigators, may analyse the observational data.

Thereafter, participants must read and confirm the informed consent. They will be given a copy of the signed document. The consent form must also be signed and dated by the investigator. It will be kept as part of the participants study records.

Written informed consent will be obtained from all participants without limiting time for signature. Participants who are candidates for enrolment into the study will be evaluated for eligibility during the screening visit (inclusion, exclusion criteria). Screening visit will consist of

- Assessment of medication history

- Vital signs (blood pressure / heart rate) will be taken with the participant having been in a seated position for at least 5 minutes.
- Height / weight (for calculation of BMI)

A pregnancy test will follow in case participants are not sure whether they are pregnant or not. Pregnancy testing will be performed in a urine sample according to instructions of AxaClear®, Axapharm.

The following questionnaires will be used to assess possible psychiatric disorders:

- Sociodemographic questionnaire
- Mental health questionnaire
- Depressive symptoms will be assessed with the self-rating questionnaire MADRS-S (Schmidt1988). This scale consists of 9 items assessing participants' mood, feelings of unease, sleep, appetite, ability to concentrate, initiative, emotional involvement, pessimism and zest for life. Each item is scored between 0 and 3. The total score is calculated by summing the answers of the nine items, ranging between 0 and 27 (higher scores indicate increased impairment).

Screening failures equal to participants not meeting all inclusion criteria or meeting one or more of the exclusion criteria. Excluded participants will be listed on a screening failure log.

9.3.1 Cognitive testing visit 1 and visit 2

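### The hypersensitivity exclusion names only propylene glycol, although both e-liquids list other inhaled components, and no listed procedure shows how 'Healthy' is checked for allergy or airway disease

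*Combined protocol and SAP*

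**What the plan says.** The allergy rule is the same in section 7.1 and in the synopsis: "Known hypersensitivity or allergy to propylene glycol". No other ingredient appears in an exclusion for hypersensitivity.

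Section 8.1.1 gives the CBD liquid as "5% CBD (low-temperature extracted Cannabidiol from Cannabis sativa L., purity 99%), Glycerine (vegetable), Propylene glycol, water". Section 8.1.2 gives the control liquid as "Foodstuff fragrance additives, 80% Glycerine (vegetable), 20%Propylene glycol". The design is a cross-over and section 8.3 requires the filled 0.25 mL tank to be vaped, so each participant is scheduled to inhale both liquids.

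Section 7.1 opens its inclusion criteria with 'Healthy' and does not define it. The synopsis list of inclusion criteria leaves it out, although the synopsis title and primary objective refer to healthy subjects.

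The screening steps in section 9.3.1 are "Assessment of medication history", blood pressure and heart rate, height and weight, a urine pregnancy test if the participant is unsure, and three questionnaires whose stated purpose is to detect psychiatric disorders. The study schedule adds a concomitant medication item and a 1-minute eligibility check at visit 1. A 10-minute telephone screening of the criteria comes before these. Section 3.7 names sedation as the risk and says nothing on allergic or airway reactions.

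**The concern.** By writing the propylene glycol criterion, the sponsor has accepted that a known allergy to an inhaled ingredient should keep a volunteer out. The protocol does not explain why the rule stops at one ingredient when section 8.1 lists several. The rule is therefore narrower than the products it is meant to cover.

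What is at stake is participant safety. A volunteer who already knows of an allergy to another component could be exposed when one question on the telephone would have identified the problem. Because the route is inhalation, it also matters how 'Healthy' is established for the airways, and the documents do not say.

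**Working it through.** The plan gives no figure on this point and no calculation applies. The check sets the ingredient lists against the eligibility and screening text.

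**Step 1: components against the exclusion.**

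| Component listed (water omitted) | CBD liquid (8.1.1) | Control liquid (8.1.2) | Named in the allergy exclusion (7.1, synopsis) |
|---|---|---|---|
| Hemp-extracted CBD | yes, 5% | no | no |
| Glycerine | yes, share not given | yes, 80% | no |
| Propylene glycol | yes, share not given | yes, 20% | **yes** |
| Fragrance additives | not itemised | yes, share not given | no |

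One of four component types is named. In the control liquid the exclusion names the 20% ingredient and not the 80% one. The stated shares add to 80% + 20% = 100%, so no share is left for the fragrance additives, and section 8.1.2 does not say what they are. Section 8.1.1 gives citrus fruits as the label and taste of the CBD liquid but itemises no flavouring. Whether that liquid contains one cannot be read from the list.

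**Step 2: a volunteer with a known allergy to an unnamed component.** Take someone with a known allergy to glycerine, hemp or a flavouring who has no other condition. This person can reasonably be called healthy and can satisfy the blood pressure, BMI, age and language criteria. Going through the exclusions in section 7.1 one by one, none applies.

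**Step 3: a volunteer with airway disease.** Here 'Healthy' does apply, and the person is not eligible by rule. The question is how the site would find out.

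- The exclusion "Long-term systemic medication or topical steroids to treat an underlying disease within last 3 months", together with the medication history and the concomitant medication item, would catch some treated cases. Occasional use of an inhaler need not meet that exclusion, although the medication items might bring it to light.
- None of the other steps in section 9.3.1 or the schedule is described as covering respiratory or allergy history.
- The telephone screening form and the source checklists mentioned in section 12.1.2 are not in the documents, so a relevant question may exist there.

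The documents therefore support the statement that no listed procedure asks. They do not show that the site never asks.

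**The case against.** The case on the other side has real force.

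- **The exclusion list may be open.** Section 7.1 introduces it with "will lead to exclusion of the participant, for example", so other grounds could be applied. This stands as a matter of wording. But section 7.2 has staff apply the criteria by telephone and section 12.3 has them monitored, and an unwritten criterion can be neither asked consistently nor monitored.
- **'Healthy' is checked twice.** The criteria are applied by telephone and again at visit 1, and medication is reviewed. This stands for airway disease, where the defect is an undefined term. It does not settle Step 2, because a person with a known ingredient allergy can be healthy.
- **The documents state no reaction risk for the other components.** This is correct, and it limits how serious the point can be. The argument rests only on the sponsor's own rule for propylene glycol and on the ingredient lists.

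A reader might also infer three stronger things that the text does not support:

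- *That propylene glycol allergy is the only exclusion relevant to inhalation.* Section 7.1 also excludes people who smoke more than 5 cigarettes per day.
- *That susceptible people are made to vape both liquids.* The full tank is a protocol requirement, but section 7.4 allows withdrawal at any time without a reason. Adverse events that prohibit testing and "Impossibility to vape 0.25mL e-Liquid" both lead to withdrawal. Vaping is supervised (8.4), and section 9.3 has participants interviewed about their wellbeing at the end of each test day.
- *That withdrawals after a reaction bias the comparison of CBD with placebo.* Efficacy is analysed in completers (11.4.1) and drop-outs are replaced (7.4), but nothing shows that such withdrawals would relate to the treatment difference. Section 7.4 also has safety analysed in everyone who received study medication. Whether a completer analysis is appropriate is a separate question.

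**Conclusion.** The point holds in a narrow form. The allergy criterion in section 7.1 and the synopsis does not match the ingredient lists in section 8.1: it names one of four listed component types, and a known allergy to any of the other three meets no listed exclusion. 'Healthy' formally bars airway disease but has no definition and no listed allergy or respiratory check, and it is absent from the synopsis criteria list.

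The count of one in four describes the text and does not measure risk. A reader might want the number of the 34 participants likely to be affected, but the documents give no rate of component allergy or airway disease, so no estimate is offered.

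The conclusion assumes that the criteria are applied as written and that the listed procedures are the ones performed. If the telephone form already asks about allergies and airways, the screening part reduces to documenting that, and the mismatch in the wording of the criterion remains. This is an inexpensive safety improvement with no demonstrated effect on the primary comparison, the power or the analysis.

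**What to change.** 1. Reconcile section 7.1 and the synopsis with section 8.1 by widening the criterion to known hypersensitivity or allergy to any component of either e-liquid. List the components so that volunteers can answer. This means establishing what the fragrance additives are and whether the CBD liquid contains a flavouring.
2. Put the question in the telephone screen and in the visit 1 eligibility check, and show it in section 9.3.1.
3. Carry 'Healthy' into the synopsis list of inclusion criteria, and have the sponsor state how it is checked for airway disease, given the inhaled route. The specific respiratory rule is for the sponsor to set. If the telephone form already covers this, a reference to it is enough.
4. Make clear whether the exclusion list in section 7.1 is complete, since its introduction presents it as examples.

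The cost is a change of wording, one or two questions added to an existing 10-minute call and a 1-minute check that may need slightly longer, possibly an enquiry to the manufacturers about flavourings, and a few volunteers turned away. Endpoints, sample size and analysis do not change.

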7.2 Recruitment and screening

Study participants will be searched at the University of Basel, Bern and Zurich by mean of flyers as well as advertisements via the websites psycho.unibas.ch, markt.unibas.ch and marktplatz.uzh.ch, newspapers, Basler Verkehrsbetriebe (BVB) and Facebook. We will also invite former participants of unrelated studies in our Division of Cognitive Neuroscience by e-mail.

After contacting our subinvestigator via e-mail, a study team member will call the volunteer to inform him/her about the study. If the person meets all inclusion criteria and none of the exclusion criteria and is interested in participating, a date for the first visit will be fixed, the informed consent (Probandeninformation und Einverständniserklärung) will be sent, and the telephone screening documents will be filed as part of the SD in the participant's dossier. The telephone screening documents of participants, who are not eligible for the screening, will be shredded.

A study compensation of CHF 70 including travel expenses will be paid during visit 2.

7.3 Assignment to study groups

After informed consent, each participant will be assigned to a participant number. Eligible participants will be randomly allocated to either receive CBD or placebo first at visit 1 (see 6.1.3).

7.4 Criteria for withdrawal / discontinuation of participants

Participants have the right to withdraw from the study at any time for any reason without being obliged to give reason. There will be a final interview regarding their actual wellbeing after withdrawal for whatever reason. The subinvestigator also has the right to withdraw participants from the study if it is in the best interest of the participant.

The following reasons result in withdrawal:

- Adverse events prohibiting cognitive testing (e.g. nausea, headache)
- Single administration of psychoactive drug within 5 days before visit 2
- Non-Compliance
- Severe protocol violations
- Administrative problems
- Impossibility to vape 0.25mL e-Liquid
- Alcohol intake within 12 hours before visit 2

Withdrawal date and reason (if known) will be listed in the participant enrolment log. Safety data will be analysed for all participants, who received study medication.

A team member, who is not involved in the data sampling procedure, will provide the study leader with replacement e-liquid tanks, in case drop-outs have to be replaced. This way, the randomization order of the randomization list can be maintained. Drop-outs will be replaced until data of 34 participants are completed.

8. STUDY INTERVENTION

8.1 Identity of Investigational Products (treatment / medical device)

8.1.1 Experimental Intervention (treatment / medical device)

Single vape of 0.25mL of CBD e-Liquid containing: 5% CBD (low-temperature extracted Cannabidiol from Cannabis sativa L., purity 99%), Glycerine (vegetable), Propylene glycol, water

Brant: Pharma Hemp, Slovenia, <https://pharmahemp.store/shop/e-liquids/cbd-e-liquid-5-10ml/>

Label: CBD E LIQUID 5% Citrus Fruits

Color: Light orange

Taste: Citrus Fruits

Vaporizer: Canna Vape Kit

8.1.2 Control Intervention (standard/routine/comparator treatment / medical device)

Single vape of 0.25mL of La Baronne Jaune e-Liquid containing: Foodstuff fragrance additives, 80% Glycerine (vegetable), 20%Propylene glycol

Brant: BORDO2, France, <https://www.bordo2.com/oh-my-god/la-baronne-jaune-oh-my-god>

Label: LA BARONNE JAUNE

Color: Colorless

Taste: Lemon and madeleines

Vaporizer: Canna Vape Kit

8.1.3 Packaging, Labelling and Supply (re-supply)

We will use commercially available e-liquids:

- **CBD e-liquid** provided with a Certificate of Analysis containing 5.079% w/w CBD and < 0.05% w/w THC
- **La Baronne Jaune e-liquid**

In preparing the Vaporization tanks we shall adhere to the Schweizerische Hygieneverordnung: <https://www.admin.ch/opc/de/classified-compilation/20143394/index.html>, concerning especially:

- Cleanliness of work surface and all used utensils
- Use of products before date of expiry
- New vaporization tanks for each participant
- Protection from contamination by using new syringes to fill the tanks
- Temperature control

8.1.4 Storage Conditions

Filled tanks are kept at room temperature between 15°C and 25°C (controlled by Logtag® data logger) in a dark with badge restricted room until consumption.

8.2 Administration of experimental and control interventions

8.2.1 Experimental Intervention

It takes approximate 15 minutes to vape 0.25mL of an e-Liquid. We use a CBD e-Liquid with a high amount of CBD to reach a low dose (12.5mg CBD). This vape time is reasonable for e.g. students vaping before an exam.

Pharma Hemp produces CBD-Liquids with CO₂ fluid extraction. This procedure gently extract CBD from Cannabis sativa L. yielded purest CBD oil.

8.2.2 Control Intervention

Bord'O2 is a French e-Liquid brand from Bordeaux. It is rated as the top 3 e-Liquid brands according to the website vapoteurs.net. La Baronne Jaune tastes similar to CBD e-Liquid. So the use of this e-Liquid seems very suitable as comparator.

8.3 Dose / Device modifications

The filled tank (0.25mL) has to be vaped.

8.4 Compliance with study intervention

Participants will vape e-liquid under supervision of a study member.

8.5 Data Collection and Follow-up for withdrawn participants

Withdrawn participants will be paid off the compensation. In case of an AE it will be followed up until resolution.

8.6 Trial specific preventive measures

One week before and during the entire Study participants are not allowed to consume CBD in any form like smoking, vaping, eating (e.g. sweets, ice cream, chocolate containing CBD, CBD capsules), drinking (e.g. teas, beer, milk containing CBD), or using CBD lotions, massage oil, tinctures, sprays or joss-sticks.

We will register possible consumption. Coffee and black tea is permitted in the individual amount. Subjects should keep regular sleep habits.

Alcohol, psychoactive drugs are not permitted within the above (7.4) specified time period.

